7.5.2 Safety endpoints

All safety endpoints will be analysed using the safety analysis set.

Primary safety endpoint

The primary safety endpoint is defined as the number of AEs 17 weeks after implantation.

All AEs will be coded using the most recent version of Medical Dictionary for Regulatory Activities (MedDRA).

Secondary safety endpoint

The number of **ADEs** 17 weeks after implantation will be summarised as described for AEs.

7.5.3 Usability endpoints

All usability endpoints will be analysed using the FAS.

Development in discomfort over time

Data from questionnaires regarding discomfort related to the implanted device will be tabulated and presented by week and discomfort category and compared over time (visit 5 to visit 10).

Assessment of alarm fatigue

Data from questionnaire regarding alarm fatigue at visit 12 will be tabulated and presented by category of sensitivity and false alarm(s).

User satisfaction

Subject user satisfaction at visit 8 will be summarised based on the specific questionnaire.

Usage of external device

The mean number of hours the hyposafe H02 day or night device has been connected to the implant from visit 4 to visit 10 will be summarised. Summaries will be presented for daytime and night-time, separately.

Response to hypoglycaemia alarm

The number of preventive actions, i.e. the number of hypoglycaemia alarms where subject was able to take preventive action as instructed (acknowledge the alarm by key press, measure blood glucose, and in case of low blood glucose; ingest a carbohydrate rich meal) compared to the total number of hypoglycaemia alarms from visit 5 to visit 10 will be tabulated.

8 Ethics

The study will be conducted according to the Declaration of Helsinki (23) and approved by the local ethical committee before commencement. The use of the hyposafe H02 must be approved by the Danish Health and Medicines Agency before initiation. Only information relevant for the study will be collected. As UNEEG™ medical is a private data responsible the current private health research project will not been notified to the Danish Data Protection Agency. Data will be handled in accordance with the Act on Processing of Personal Data.

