2.1.2 Secondary objective

Usability

To evaluate the usability of the hyposafe H02 during everyday activities in subjects with type 1 diabetes.

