2.2 Endpoints

Primary performance endpoints

- Sensitivity: Proportion of spontaneous hypoglycaemic episodes detected by the hyposafe H02 compared to the total number of validated¹ spontaneous hypoglycaemic episodes after 12 weeks of monitoring (from visit 5 to visit 10)
- Positive predictive value: Proportion of validated¹ spontaneous hypoglycaemic episodes detected by the hyposafe H02 compared to the total number of alerts from the hyposafe H02 after 12 weeks of monitoring (from visit 5 to visit 10)

Secondary performance endpoints

- Overall sensitivity: Overall proportion of hypoglycaemic episodes detected by the hyposafe H02 compared to the total number of validated² hypoglycaemic episodes after 12 weeks of monitoring (from visit 5 to visit 10)
- Overall positive predictive value: Overall proportion of validated² hypoglycaemic episodes detected by the hyposafe H02 compared to the total number of alerts from the hyposafe H02 after 12 weeks of monitoring (from visit 5 to visit 10)
- Sensitivity: Proportion of insulin-induced hypoglycaemic episodes detected by the hyposafe H02 compared to the total number of insulin-induced hypoglycaemic episodes

¹ Validated by self-measured blood glucose (SMBG) or clinical hypoglycaemia according to subject's experience

² Validated by self-measured blood glucose (SMBG), plasma glucose (PG) or clinical hypoglycaemia according to subject's experience

- Positive predictive value: Proportion of insulin-induced hypoglycaemic episodes detected by the hyposafe H02 compared to the total number of alerts from the hyposafe H02
- Number of participants with a satisfactory EEG Quality test
- Change in impedance (from visit 5 to visit 10)
- Number of device complaints (from visit 4 to visit 10)
- Mean glucose level at the time of a hypoglycaemia alarm

Primary safety endpoint

- Number of AEs 17 weeks after implantation (from visit 3 to visit 12)

Secondary safety endpoint

- Number of adverse device effects (ADEs) 17 weeks after implantation (from visit 3 to visit 12)

Secondary usability endpoints

- Development in discomfort over time (visit 5 to visit 10)
- User satisfaction (visit 8)
- Mean number of hours of use per hyposafe H02 device (from visit 4 to visit 10)
- Response to hypoglycaemia alarm (from visit 5 to visit 10)
- Assessment of alarm fatigue (visit 12)

3 Study design - overview

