7.5 Endpoint analysis

7.5.1 Performance endpoints

All performance endpoints will be analysed using the FAS as well as the PP analysis set.

Primary performance endpoint

The primary performance endpoints are defined as the sensitivity and positive predictive value of the hyposafe H02 based on spontaneous hypoglycaemic episodes.

Spontaneous hypoglycaemic episodes are recorded by subjects in the log book throughout the study. This includes information on blood glucose measurements before treating the episode, alarms given by the hyposafe H02 device and information on whether the subjects was able to treat him/herself or was asleep when the episode occurred.

A hypoglycaemic episode will be characterised as treatment emergent if the onset of the episode is on or after the first day the hyposafe H02 device switched to “*alarm on*”-mode and no later than the last day of the wearing the external device. Data on treatment emergent hypoglycaemic episodes are presented in terms of the number of subjects with at least one episode (N) and the number of episodes (E).

Hypoglycaemic episodes will be defined as nocturnal (i.e. during night-time) if they occur during sleep (as reported by the subject) and/or are registered by the hyposafe H02 night device.

Data from blood glucose measurement and clinical hypoglycaemia (according to subject’s experience) will be used by UNEEG™ medical to classify a hypoglycaemic alarm according to categorisation displayed in Table 2 (true and false, positive and negative hypoglycaemia alarms). As blood glucose values are lower than plasma values, a constant factor of 1.11 is used to convert concentration in whole blood to the equivalent concentration in plasma (25).

Sensitivity and positive predictive value will be calculated for daytime and night-time, separately.

Secondary performance endpoints

Insulin-induced hypoglycaemia is performed twice for each subject, with frequent assessments of plasma glucose levels. As the number of spontaneous hypoglycaemic episodes reported during the study may be relatively small, data from the insulin-induced hypoglycaemia will be added to calculate the overall **sensitivity and positive predictive value** of the hyposafe H02 (spontaneous and insulin-induced hypoglycaemia episodes) after 12 weeks of monitoring (from visit 5 to visit 10).

The sensitivity and positive predictive value will also be calculated based data from the insulin-induced hypoglycaemic episodes only.

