The hypoglycaemic alarms will be classified according to categorisation displayed in Table 2 (true and false, positive and negative hypoglycaemia alarms), and presented as described for primary performance endpoint.

Table 2 Categorisation of hypoglycaemic episodes

Episodes categorised as			
PG > 3.9mmol/l	+ alarm	+/- clinical hypoglycaemia ^{a)}	False positive 
	- alarm	+/- clinical hypoglycaemia ^{a)}	True negative 
PG 2.0 – 3.9mmol/l	+ alarm	+/- clinical hypoglycaemia ^{a)}	True positive 
	- alarm	+ clinical hypoglycaemia ^{a)}	False negative 
		- clinical hypoglycaemia ^{a)}	True negative 
PG < 2.0mmol/l	+ alarm	+/- clinical hypoglycaemia ^{a)}	True positive 
	- alarm	+/- clinical hypoglycaemia ^{a)}	False negative 
PG not measured	+ alarm	+ clinical hypoglycaemia ^{a)}	True positive 
		- clinical hypoglycaemia ^{a)}	Not categorised 
	- alarm	+ clinical hypoglycaemia ^{a)}	Not categorised  False negative ^{b)} 

^{a)} According to subject (No strict definition is given)

^{b)} If hypoglycaemic episode was severe (i.e. requiring assistance from third person whether being help for carbohydrate ingestion, glucagon injection or contact to health care person), the episodes should be characterised as false negative

PG; plasma glucose

Data from **EEG quality test** at the visit 4 and visit 10 will be compared graphically.

The **impedance** is expected to be below 5 kOhm at all times. No trend in the measurements for each subject should be apparent over time, except perhaps a small decline in the beginning. Any change in impedance over time (from visit 5 to visit 10) will be summarised descriptively and presented by subject.

The **number of device complaints** will be tabulated and presented by device part.

Mean blood, plasma or interstitial **glucose level at the time of an alarm** will be summarised for insulin-induced hypoglycaemia and spontaneous hypoglycaemic episodes, separately.

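### The alarm-response endpoint pools alarms from insulin-induced sessions with everyday alarms, so it does not measure the everyday response that the usability objective asks for

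*Combined protocol and SAP*

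**What the plan says.** Section 2.2 lists the endpoint among the secondary usability endpoints as "Response to hypoglycaemia alarm (from visit 5 to visit 10"). Section 7.5.3 defines it. The numerator is "the number of hypoglycaemia alarms where subject was able to take preventive action as instructed", where the instructed action is to acknowledge the alarm by key press, measure blood glucose and, if it is low, eat. This count is "compared to the total number of hypoglycaemia alarms from visit 5 to visit 10 will be tabulated". Neither numerator nor denominator is limited to a type of alarm or a setting.

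The objective that this endpoint serves (2.1.2) is narrower: "To evaluate the usability of the hyposafe H02 during everyday activities in subjects with type 1 diabetes". The performance objective in 2.1.1, by contrast, names both everyday activities and insulin-induced hypoglycaemia.

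On the sessions themselves, 7.5.1 states: "Insulin-induced hypoglycaemia is performed twice for each subject, with frequent assessments of plasma glucose levels". The same section describes the overall sensitivity and positive predictive value as covering "spontaneous and insulin-induced hypoglycaemia episodes) after 12 weeks of monitoring (from visit 5 to visit 10"). The mean glucose level at an alarm, another endpoint computed on alarms, "will be summarised for insulin-induced hypoglycaemia and spontaneous hypoglycaemic episodes, separately".

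**The concern.** An induced session differs from daily life: glucose is lowered on purpose and plasma glucose is measured frequently by the site. What a subject does when the alarm sounds there is not evidence of what the same subject does at home, at work or asleep. A single pooled proportion cannot be separated afterwards by a reader of the report.

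The plan keeps the two settings apart for the primary performance endpoints and for glucose at alarm, but not here, where the objective most plainly calls for it. At stake is the meaning of one usability figure in a report that section 8.10 says will be used in further development and approval of the device.

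**Working it through.** The plan gives no expected alarm count, response rate or precision for this endpoint, so there is no figure to reproduce. The check has two parts.

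**1. Do session alarms fall inside the definition?**

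- Alarms in sessions are counted as alarms. Section 2.2 includes the endpoint "Proportion of insulin-induced hypoglycaemic episodes detected by the hyposafe H02 compared to the total number of insulin-induced hypoglycaemic episodes" and a matching positive predictive value.
- Section 7.5.1 counts the induced episodes within visits 5 to 10, the same window as the response endpoint.
- The flow chart (Table 1), as extracted, marks induced hypoglycaemia under visits 7 and 11. Its later columns look displaced: the EEG quality test appears under visits 5 and 11, while 7.5.1 says visits 4 and 10. This may come only from the PDF extraction. Even taken at face value, the visit 7 session lies inside the window.

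So one or two sessions per subject contribute alarms to the endpoint as written.

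**2. What does pooling do to the figure?**

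Let D and I be the numbers of everyday and session alarms, and pd and pc the proportions followed by the instructed action in each setting.

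- Pooled response = (D × pd + I × pc) / (D + I)
- Shift from the everyday response = I / (D + I) × (pc − pd)

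The sign depends only on whether pc is below or above pd. The size depends on the share of session alarms, I / (D + I).

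From the documents: at least 12 completing subjects (3.1, 7.1) and two sessions each (7.5.1). Assumed: pd = 75%, one alarm per session, and the values of D. Then I = 12 × 2 = 24, or 12 × 1 = 12 if only one session per subject falls in the window.

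| D | I | Session share | Pooled, pc = 0 | Pooled, pc = 1 |
|---|---|---|---|---|
| 60 | 24 | 24/84 = 28.6% | 45/84 = 53.6% | 69/84 = 82.1% |
| 60 | 12 | 12/72 = 16.7% | 45/72 = 62.5% | 57/72 = 79.2% |
| 200 | 24 | 24/224 = 10.7% | 150/224 = 67.0% | 174/224 = 77.7% |
| 1,008 | 24 | 24/1,032 = 2.3% | 756/1,032 = 73.3% | 780/1,032 = 75.6% |

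The last row is 7 everyday alarms per subject-week (7 × 12 weeks × 12 subjects). If pc = pd = 75%, the pooled figure is 75% in every row. In the first row the shift runs from 0.286 × (0 − 0.75) = −21.4 points to 0.286 × (1 − 0.75) = +7.1 points.

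**The case against.** Three arguments can be made for leaving the plan alone.

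*The intention may already be everyday alarms only.* The objective says so. Section 2.2 also gives the positive predictive value for spontaneous episodes a similarly unqualified denominator, and 7.5.1 presents the induced data as something added for the overall figures. This is a fair reading of intent, and it stands as a reason to call the change minor. It does not remove the problem: an analyst who follows 7.5.3 as written will count the session alarms.

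*The effect may be negligible.* This stands as a possibility. The denominator includes false alarms, and with frequent everyday alarms the shift is a point or two at most. The remark in 7.5.1 that spontaneous events may be relatively few concerns episodes, not alarms, so it does not show that everyday alarms will be few.

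*The stakes are low.* The endpoint is secondary and only tabulated, and section 7 plans no comparative analyses. This also stands.

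A reader might go the other way and infer that the pooled figure understates the everyday response, because a supervised subject has little occasion to complete the instructed steps, or that better detection of induced episodes must lower it. The documents do not support this. The numerator is as unrestricted as the denominator, and nothing states what subjects do, or are prompted to do, when an alarm sounds in a session. They could act less often because staff manage the episode, or more often because they are awake and observed.

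**Conclusion.** The point holds as a mismatch between endpoint and objective. As written, the alarm-response endpoint mixes alarms from supervised induced sessions with everyday alarms, while the usability objective is confined to everyday activities. The direction of the resulting error is unknown.

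The illustrative ranges rest on the assumed 75% everyday response, one alarm per session, the assumed everyday alarm counts and the two extremes for session response; none of these comes from the documents. They show that the distortion could be material if everyday alarms number in the tens and is trivial if they number around a thousand. It is a minor point about a descriptive secondary endpoint, worth correcting because the correction is cheap.

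**What to change.** In 2.2 and 7.5.3, add one clause that limits both the numerator and the denominator of the alarm-response endpoint to alarms outside the insulin-induced sessions. Tabulate session alarms on a separate line, counting them neither as response nor as non-response in the everyday figure.

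No new data are needed. The induced-only sensitivity and positive predictive value, and the split of glucose at alarm, already require each alarm to be attributed to an induced session or not, and the same attribution can be used here. The cost is slightly fewer alarms in the main tabulation. With the restriction, the endpoint equals the observed everyday response by construction. No study procedure changes.

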8.1 Subject benefit and risks

A risk analysis according to ISO 14971 “Application of risk management to medical devices” has been conducted. Risks have been minimised or eliminated through appropriate design control.

Impaired awareness of hypoglycaemia associated with increased morbidity and mortality, is a serious problem for many patients with type 1 diabetes, and it is believed that the potential benefit of a hypoglycaemia alarm system outweighs the potential risks in the current study.

The subject participating in this study cannot be guaranteed benefits of the participation. If the hypoglycemia alarm works as intended, subjects with the alarm function switched on may experience an increased security at hypoglycaemia.

An external energy source powers the implant via an inductive link. There is no risk of transfer of power from the energy source to the surrounding tissue of the subject. No radioactive substances are used in the study.

Foreseeable AEs and anticipated ADEs are infection (estimated risk: 0.5%), headache (estimated risk: 10%), seizures (estimated risk: 0.5%), and phlebitis (estimated risk: 1-2%).

8.2 Subject insurance

Product liability and no fault clinical trial assurance covering the duration of the study are in place, to enable compensation in the event of an injury to a participating subject.

8.3 Informed consent

Study subjects will be recruited by advertising or by personal contact to the subject in the outpatient clinics. The information sheet will be sent to or given to the participant at least 3 days before the screening visit. Participants will be encouraged to bring a friend or a family member for the screening visit at the study site. The study procedures will be explained to the participant by qualified personnel and the information sheet will be reviewed with the participant under undisturbed conditions in a quiet room reserved for this purpose. A voluntary, signed and dated informed consent form must be obtained from the subject prior to any study related activities.

The investigator is responsible for ensuring that no subject is subjected to any study related examination or activity before the subject has given his/her written informed consent. The written informed consent must be signed and dated by the person who seeks the consent.

8.4 Early termination or suspension of the investigation

If the sponsor or the safety committee find continuation of the study incompatible with the safety of the study subjects due to any safety related issues of the study product or the study procedure the study will be terminated or postponed until these issues have been solved.

If a study is prematurely terminated or suspended, the investigator should promptly inform the subjects and assure appropriate follow-up. Furthermore, the investigator and/or UNEEG™ medical should promptly inform the ethics committee and provide a detailed written explanation. The regulatory authorities should be informed according the regulations.

8.5 Changes to clinical investigation plan or related procedures

All substantial changes to the clinical investigational plan must not be implemented before approval/favourable opinion unless necessary to eliminate immediate hazards to the subjects. All changes to the clinical investigation plan require notification to the ethics committee and the

competent authority. No changes in the study procedures must be implemented without mutual agreement of the investigator and the sponsor.

8.6 Deviations from clinical investigation plan

Deviation to the clinical investigational plan should be avoided. If deviations occur, the investigator must inform the sponsor who is responsible for analysing and assessing the implication of the deviation. Any deviation from the clinical investigation plan must be documented stating the explanation for the deviation, the date and any actions taken.

Significant deviations compromising or potentially compromising the safety of the subjects, enrolment of non-eligible subjects or any deviation, which significantly compromises the outcome of the study, must be reported to the ethics committee within the appropriate timelines indicated by the ethics committee.

8.7 Audit and supervision

Investigator sites and study documentation may be subject to quality assurance audits during the course of the study. In addition, regulatory bodies at their discretion may conduct inspections, during and after study completion.

8.8 Data and quality management

CRF data collected will be subject to data quality control measures in compliance with all applicable data management procedures. Edit checks will be applied to identify discrepant data. All CRFs will be audited against corresponding database output to ensure accuracy. Data management documentation will be generated and maintained throughout the process including the data management plan and associated project binders.

8.9 Safety committee

UNEEG™ medical will constitute an internal safety committee to perform ongoing safety surveillance.

8.10 Reporting of results

The results of the investigation will be summarised in a report to be used in the further development and approval of the device. The report will be forwarded to the ethics committee and competent authorities at the end of the investigation. The main findings of study will be submitted for publication in a peer reviewed journal or made public available www.clinicaltrials.gov.

